6.1.2 Exclusion criteria

- Participants must be able to speak English at a basic level.
- Participants must have good internet access to take part in the online consultations.
- Participants have not had experience with the CAMHS referral process.

We will inform participants during the consent process (i.e. in the PIS and subsequent discussions) that there may be discussion which they could find upsetting, and we have a distress protocol in place for if anyone needs additional support, but that this should be considered when agreeing to take part in the study.

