Research Question/Aim(s)	
We aim to develop a simple, clear way for children to get the right support for their mental health problems when they need it. We aim to solve the problems people told us about in EN-CAMHS 1 (NIHR 131379) and to improve the quality of referrals made to CAMHS.
 
Research Questions:
 
 1. Using the findings from NIHR HS&DR-funded EN-CAMHS 1 and stakeholder consultation, can we develop a set of national standards for digital CAMHS referral processes?

	
 2. Can we translate the prioritised features from EN-CAMHS 1 of a digitally-led, intelligent CAMHS referral process into a usable, acceptable and widely accessible platform that is nationally standardised, locally adaptable and sustainable? 3. Can we address concerns about digital health equity through the newly developed CAMHS referral mechanisms? 4. How do referrers, including GPs, school staff and children/young people/families perceive the usability and acceptability of the digital tool? 5. How do referrers use and engage with the tool? 6. How do rates of successful referrals with the tool compare to traditional modes of referral?
--	--

FUNDING AND SUPPORT IN KIND

FUNDER(S) (Names and contact details of ALL organisations providing funding and/or support in kind for this study)	FINANCIAL AND NON FINANCIAL SUPPORT GIVEN
National Institute for Health Research Health Services and Delivery Research Programme	£1,259,268.30

ROLE OF STUDY SPONSOR AND FUNDER

Department of Health definition of a sponsor: An individual, organisation or group taking on responsibility for securing the arrangements to initiate, manage and finance a study. A group of individuals and/or organisations may take on sponsorship responsibilities and distribute them, by agreement, amongst the members of the group, provided that, collectively, they make arrangements to allocate all the responsibilities that are relevant to the study.

Summary of Sponsor Responsibilities:

- Taking responsibility for putting and keeping in place arrangements to initiate, manage and fund the study.
- Confirming that everything is ready for the research to begin.
- Satisfying itself the research protocol, research team and research environment have met the appropriate scientific quality assurance standards.
- Satisfying itself the study has ethical approval before relevant activity begins.

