EN-CAMHS 1 stakeholders recommended we implement a digital solution to address the current problems of poor communication, missing information, poor data quality and lack of guidance for families about what to expect of the referral journey. The design and development of the digital tool will specifically address the accessibility needs of referrers. We intend to explore issues of digital accessibility in the consultations (WP1) and in the co-design workshops with participants. We shall also consider the three key elements of digital exclusion: lack of digital access; lack of digital skills; lack of confidence to use digital. We will explore these challenges in the co-design workshops, with stakeholders in consultation and with our advisory groups. The digital tool will supplement rather than supplant traditional modes of referral; traditional (e.g. paper based) modes of referral will remain. However, we anticipate that our digital tool will enable more people to make more successful referrals than before.

We shall also **generate new knowledge** about the patterns of referrals into CAMHS, by automating data collection through the digital tools and thereby enabling services and NHS England to understand referral and treatment data in greater detail than ever before. We see **enormous potential** in this project and its learnings/outputs for cross-pollination to **other services experiencing similar problems**.

1. Referrals overwhelming CAMHS

- We **cannot** increase CAMHS staff levels or change what it can provide.
- We **can** make the referral process work better and with greater satisfaction for referrers and for those being referred.
- We **can** increase confidence in CAMHS alternatives and increase follow-through into CAMHS alternatives.
- We **can** help CAMHS prioritise the needs of those it is designed to help.

2. Quality of referrals is poor

- We **can** provide clear, accessible guidelines to make appropriate referrals.
- We **can** validate input on the referral form and ensure all required information is completed pre-submission.
- We **can** raise awareness about what a good referral is.
- We **can** educate people about common referral mistakes.

3. Poor experience of referral

- We **can** explain the referral process clearly.
- We **can** outline key steps in the referral journey and inform people about the expected waiting times for the local CAMHS triage process.

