3 RESEARCH QUESTION/AIM(S)

Our overarching aim is to improve the CAMHS referral process for CYP, their families and carers, as well as for health, education and CAMHS professionals so that CYP receive the help they need as quickly as possible.

Research questions:

1. Using the findings from EN-CAMHS 1 and stakeholder consultation, can we develop a set of national standards for digital CAMHS referral processes?
2. Can we translate the prioritised features from EN-CAMHS 1 of a digitally-led, intelligent CAMHS referral process into a usable, acceptable and widely accessible platform that is nationally standardised, locally adaptable and sustainable?
3. Can we address concerns about digital exclusion and other identified health inequalities through the newly developed CAMHS referral mechanisms?
4. How do referrers, including GPs, school staff and children/young people/families perceive the usability and acceptability of the digital tool?
5. How do referrers use and engage with the tool?
6. How do rates of successful referrals with the tool compare to traditional modes of referral?

There are no primary nor secondary outcome measures for this study as this is a feasibility study to evaluate usage and acceptability of the co-created tool using data collected from referrers. These data will be a combination of quantitative data on usage and engagement and qualitative data from semi-structured interviews with 25 referrers.

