5 STUDY SETTING

This is a multi-site study. The referral data collection will involve 5-8 CAMHS sites from various regional providers. The collaborating sites will be selected to: target the areas of high need for CYP mental health; reflect diversity in terms of urban/rural locations; ethnicity of service user population; diversity in configuration of CAMHS services/CAMHS offer.

The stakeholder and Trust staff consultations, i.e. roundtables, focus groups, workshops and semi-structured interviews, will be held both virtually and face-to-face. Virtual consultations will be facilitated via Microsoft Teams. If any sessions are held in person, these will be held at different locations to ensure they are as accessible as possible, for example, central locations in both the South and North of England.

Quantitative data reflecting usage and engagement will be collected using inbuilt analytics.

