6 SAMPLE AND RECRUITMENT

6.1 Eligibility Criteria

6.1.1 Inclusion criteria

Throughout the project, participants will be included if they are:

- Aged 16+.
- CAMHS Stakeholders who have experience with the CAMHS referral process since 2019, these may include:
 - CAMHS Staff: we will include any staff who currently work in CAMHS services.
 - Collaborators: We will include collaborators who have direct experience of the current referral process for CAMHS.
 - CYP: We will be recruiting CYP who have been referred to CAMHS regardless of whether they were accepted into the service or not.

- Key referrers: We would ask that these individuals have had experience referring CYP to CAMHS, regardless of how many times.
- Parents/carers: we will ask parents/carers who have experience of their child or a child in their care having been referred to CAMHS, regardless of the outcome of the referral.
- CAMHS Commissioners: We will ask Commissioners who understand the current CAMHS referral processes locally or nationally, and who are involved in the funding process.
- Mental Health Leads: We will invite people with a strategic overview of the CAMHS referral process locally or nationally to share their experiences of the referral process.
- Any individuals identified through earlier WPs as key to the CAMHS referral process.
- Able to provide informed consent.
- Be proficient in English.

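### Section 6.1.2 makes good internet access an eligibility criterion with no stated offline route, which can keep people without digital access out of the WP1 and WP2 sessions meant to explore digital exclusion for RQ3

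*Protocol*

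**What the plan says.** Section 6.1.2 of the protocol, headed as exclusion criteria, includes the line "Participants must have good internet access to take part in the online consultations". No work package is named, and nothing is said about people who do not meet it. The companion inclusion list in 6.1.1 opens with "Throughout the project, participants will be included if they are", so section 6.1 reads as applying to the whole project.

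RQ3 in section 3 asks: "Can we address concerns about digital exclusion and other identified health inequalities through the newly developed CAMHS referral mechanisms". The Study Summary puts the same question in terms of digital health equity. The Rationale (section 2) undertakes to consider the "three key elements of digital exclusion: lack of digital access; lack of digital skills; lack of confidence to use digital", and says where: "We will explore these challenges in the co-design workshops, with stakeholders in consultation and with our advisory groups".

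On format, section 5 first says that the consultations will be both virtual and face-to-face, and then continues: "If any sessions are held in person, these will be held at different locations". On consent, section 6.3.2 says that the form is collected through the digital referral tool and that consent is written and electronic only. A telephone call is offered there, but for questions before consent, not as a way of taking part.

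**The concern.** An eligibility criterion is applied to people. This one turns on a characteristic that the protocol itself treats as part of the problem under study. A parent or young person without reliable internet belongs to the group named first in the Rationale's account of digital exclusion. The same person appears not to meet section 6.1.2, and the protocol states no other way in.

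At stake is the evidence base for RQ3. WP1 sets the requirements for the tool, and WP2 co-designs it and reviews its accessibility. If these activities hear only from connected people, barriers of access are described second-hand. A statement that concerns about digital exclusion were addressed would then have thin support on that element.

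**Working it through.** No arithmetic settles this. The protocol uses no power calculation and gives no figure for how many stakeholders lack good internet access. The check is whether the relevant sections, read together, leave such a person a way to take part.

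1. **Who is covered.** The WP1 focus groups, WP2 co-design workshops and Digital Accessibility Working Group all recruit under section 6.1. From section 6.2.1 the places are 60, up to 2 × 25 = 50, and 10. That makes at most 60 + 50 + 10 = 120 places, with possible overlap of people because the accessibility group is formed from within the project.

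2. **Where lack of access is to be explored.** The Rationale names three settings: co-design workshops, stakeholder consultations and advisory groups. The first two fall under section 6.1. The advisory groups do not: section 7.4 gives them their own joining arrangements.

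3. **Is there an in-person route?** Section 5 gives two signals. One sentence says sessions will be held both ways; a later one makes in-person sessions conditional. No activity is assigned a definite in-person session, and nobody without internet access is promised a place at one.

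4. **Is there a route through consent?** Section 6.3.2 accepts electronic consent only, through the tool. Someone admitted to a face-to-face session would still have to consent digitally.

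5. **Does sampling bring these people back?** The diversity characteristics in sections 6.2.2 and 6.3.1 cover referrer type, CAMHS configuration and personal characteristics such as age, ethnicity, language and disability. Digital access, skills and confidence are not among those named.

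6. **What is not affected.** The criterion concerns access, not skills or confidence, so it bears on one of the three elements. The WP3 interviews are with referrers who have used the tool (section 4.2); that restriction follows from evaluating a digital tool and would remain if the criterion were removed.

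Steps 3 to 5 together show no assured path for a person without good internet access into the WP1 and WP2 activities counted in step 1. Step 6 limits how far the consequence reaches.

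**The case against.** The strongest reply is that the criterion is already tied to a format. Its own wording limits it to taking part online, and section 5 says plainly that consultations will also be face-to-face. On that reading, a person without internet simply attends in person. This may well be what was intended, and it softens the conflict. It does not remove it: the line stands among the eligibility criteria without that qualification, section 5 goes on to make in-person sessions conditional, and electronic-only consent is a second digital hurdle.

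A further reply is that the evidence is not lost. Much of this stands. The advisory groups (6-10 members each) are outside the criterion, and PPIE recruitment aims to include families living with deprivation. The accessibility group draws on needs identified in EN-CAMHS 1 and in co-design. Professionals can report on families they refer. Paper referral remains available, and the tool is to signpost telephone support. These protect service users and supply indirect evidence. They do not replace first-hand accounts from study participants without access.

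A reader might infer something stronger: that no one without good internet access can appear anywhere in the study, that the access element cannot be observed at all, or that a favourable answer to RQ3 is built in. The documents do not support this. A count of zero needs the broad reading of the criterion and no face-to-face attendance by such a person; the advisory groups remain a route; and the WP3 restriction has a different source. Nor is any of the success criteria in section 8.2 a digital-exclusion result that eligibility could decide in advance.

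**Conclusion.** The point holds in a limited form. Section 6.1.2, taken with the conditional wording in section 5 and the electronic-only consent in 6.3.2, can keep people without digital access out of the WP1 focus groups, the WP2 co-design workshops and the accessibility group. Most of the exploration of digital exclusion for RQ3 is planned there. First-hand evidence on the access element would then come mainly from people who are already connected.

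The size is at most 120 participant places under the criterion, and one of three elements of digital exclusion. How many people would actually be turned away cannot be derived: it depends on how the line is applied, on how many sessions are held in person, and on how common poor access is among those who respond to the adverts. None of these is fixed in the protocol. The conclusion assumes that staff apply the line as the eligibility criterion it is listed as. If the narrow reading was intended, the defect is one of wording plus the consent route, and should still be corrected.

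**What to change.** - **Section 6.1.2:** remove the internet requirement from the criteria and state it as a joining condition for online sessions only. Add that people without good internet access are not excluded and will be offered a face-to-face or telephone route.
- **Section 5:** reconcile the two statements so that face-to-face sessions are definite for WP1 and WP2. How many, and for which groups, is for the team to decide.
- **Section 6.3.2:** allow a non-electronic written consent form for these participants. Without this, the change to 6.1.2 would not achieve its purpose. Section 7.4 already accepts consent by post for the young people's advisory group, so the practice is not new to the project.
- **Demographics questionnaire** (Appendices 1 and 2): add short items on digital access, skills and confidence, so that the RQ3 evidence can be described by them. Formal subgroup comparison is not needed in samples of this size and kind.

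The cost is a protocol amendment, a few questionnaire items, some scheduling and travel, and the handling of paper consent forms. Sample sizes and design do not change.

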6.2 Sampling

6.2.1 Size of sample

In WP1, we shall recruit 60 key CAMHS stakeholders (CYP, parents and carers, key referrers and CAMHS professionals) to 6 focus groups (10 participants per group).

In WP2, we shall recruit 5-8 CAMHS providers, with 5-8 members of Trust staff from each provider to participate in a workshop (25-64 staff in total). 2 1-hour co-design workshops will also be held with 25 key referrers in each group. A maximum of 10 stakeholders shall be recruited to form the Digital Accessibility Working Group (n=10 CYP/families and professional referrers); a group formed from the project with characteristics derived from accessibility needs identified in the stakeholder co-design groups and from EN-CAMHS 1. This group shall meet twice during the co-design process to review the tool and suggest accessibility enhancements. Every effort will be made to incorporate suggestions made by this group into the digital tool, within the time and resource limitations of the project

In WP3, we shall recruit 60 key referrers across all sites for quantitative data collection. 25 of the key referrers will also participate in qualitative semi-structured interviews.

The sample size across the project will be made up of:

- WP1 - 6 focus groups - we aim to recruit 60 stakeholders (6-10 per group).
- WP2 - onboard 5-8 CAMHS providers, 1-hour co-design workshop with each provider (n=25), Accessibility working group n=10. 2 co-design workshops with up to 25 participants in each (n=50).
- WP3 - 60 referrers to use the tool, semi-structured interviews with 25 referrers.

6.2.2 Sampling technique

In WP1 and WP2, we shall use purposive sampling to recruit a diverse group of CAMHS stakeholders and Trust staff for focus groups.

In WP3, we shall use purposive sampling to include a diversity of referrers. We shall aim for diversity in terms of: type of referrer (GP, school, self-referrer, social care); CAMHS configuration (provision of service; location of CAMHS urban/rural) and by key individual characteristics of the referrer (age, ethnicity, spoken language etc). We shall aim to make the sample of referrers representative of the proportions of the different referrers that refer into CAMHS. That would mean more GPs than other referrers. The diversity of CAMHS configuration will be drawn from the data from EN-CAMHS 1 and with respect to relevant recent changes to the CAMHS landscape identified in WP1.

6.3 Recruitment

6.3.1 Sample identification

In WP1, we shall hold a combination of stakeholder specific and mixed stakeholder groups. Attendees can choose which type of group they feel most comfortable attending. Across the 6 focus groups we aim to recruit 60 participants representing a diversity of referrer type (CYP, GP, health, social care, educational professional, CAMHS workers, families), and also designed to incorporate the diversity within each referrer type found in EN-CAMHS 1. Identification and recruitment of stakeholders will be extensively supported by our partner MQ.

In WP3, we shall recruit referrers from across the study CAMHS sites. Senior stakeholder collaborators will be consulted to ensure the project achieves the most appropriate mix of CAMHS providers to optimise widespread applicability of the new tool. We shall work with 60 referrers to test the new referral process. We shall specifically aim to ensure appropriate diversity to test if the translated and culturally-sensitive materials we develop are fit for purpose.

We have not used power calculations for detecting effect sizes in this evaluation, as hypothesis testing is not the aim. Our aims are to 1) recruit participants to test different user experiences (opportunities and challenges) that arise as a result of using tool and; 2) to capture a diversity of: referrer types (GPs, school staff, social care professionals, parents/carers); within-referrer characteristics (age, gender, ethnicity, dis/ability); CAMHS provider (CAMHS configuration; rural/urban). Our purposive sampling approach will be targeted at maximising the diversity of referrers and CAMHS sites and supporting accessibility testing of the tool. Our sampling strategy will be informed by our diversity data from EN-CAMHS 1 and by the stakeholders consultations in WP1.

Identification and recruitment of CAMHS professional stakeholders will be supported by our extensive network of CAMHS collaborators. Recruitment of key referrers is supported by our school and primary care collaborators, as well as links to key referrers provided by our CAMHS sites. We will not directly target individuals, just share adverts about the study around collaborating organisations and networks.

Recruitment of CYP and their families will be supported by our CAMHS networks, adverts on social media and websites, and our third sector collaborators (MQ, Calm Connections, Anna Freud Centre).

We shall extend our focus group invitations beyond our collaborating sites to ensure we capture a wide diversity of CAMHS stakeholder perspectives.

6.3.2 Consent

All potential participants will be asked to provide informed consent to participate in any of the data collection stages i.e. roundtables, focus groups, workshops, testing the tool, quantitative data collection, or semi-structured interviews. They will be provided with a Participant Information Sheet and Consent Form.

Once a potential participant has expressed interest in taking part in the relevant data collection stage they will have the opportunity to review the Participant Information Sheet and Consent Form which are integrated into the referral form. The Information Sheet will detail the nature and objectives of the study and has been developed in accordance with NHS guidance. The information sheet and the consent form will be developed in consultation with both our YPAG and PPAG.

Participants will be given sufficient time to understand the information they are given and to weigh up the information in order to make an informed decision. They will be given the opportunity to ask any questions about the research if they want to and will be given the option of a Microsoft Teams meeting or telephone call with a member of the study team to ask any questions about the research. The Consent Form will be collected prior to the relevant data collection stage through the digital referral tool, therefore only written, electronic consent will be sought and obtained. Participation is voluntary and participants will be informed that they have the right to withdraw at any time without giving a reason. As per the Consent Form, any previous information collected from research activity participation before withdrawal will still be used in the study. As the Consent Form is integrated in the digital referral tool, participants will have 24 hours to decide whether or not to take part.

